## 7.2 PARTICIPANT DISCONTINUATION/WITHDRAWAL FROM THE STUDY

A participant may be discontinued from study treatment at any time if the participant or participant's legal guardian or the investigator feels that it is not in the subject's best interest to continue. The following is a list of possible reasons for study treatment discontinuation:

- Parental/guardian withdrawal of consent
- Subject is not compliant with study procedures
- Protocol violation requiring discontinuation of study treatment
- SAE, including significant toxicity such as severe cognitive or behavioral toxicity, impaired liver function, or impaired hematopoiesis that is deemed to be potentially or likely related to study medication

If subject must come off of study treatment, the method of CBD discontinuation will be determined based on type of reaction and/or reason for withdrawal. For example, if the participant experiences a rapidly progressive rash it would lead to abrupt cessation of CBD, but if participant experiences excess tiredness, CBD would be tapered off. A discussion of the method of cessation will occur between the participant and/or participant's parent/legal guardian and the physician.

Subjects for whom a parent/guardian has signed the informed consent form, who have received the study intervention, and subsequently withdraw, or are withdrawn or discontinued from the study will not be replaced.

### 7.3 LOST TO FOLLOW-UP

A participant will be considered lost to follow-up if he or she fails to return for 2 or more scheduled visits and is unable to be contacted by the study site staff.

The following actions must be taken if a participant fails to return to the clinic for a required study visit:

- The site will attempt to contact the participant and reschedule the missed visit within a week +/- 3 days and counsel the participant on the importance of maintaining the assigned visit schedule and ascertain if the participant wishes to and/or should continue in the study.
- Before a participant is deemed lost to follow-up, the investigator or designee will make every effort to regain contact with the participant (where possible, 3 telephone calls, secure email, and, if necessary, a certified letter to the participant's last known mailing address or local equivalent methods). These contact attempts will be documented in the participant's medical record or study file.
- Should the participant continue to be unreachable, he or she will be considered to have withdrawn from the study with a primary reason of lost to follow-up.

## 8 STUDY ASSESSMENTS AND PROCEDURES

### 8.1 EFFICACY ASSESSMENTS

#### Primary Endpoint

*Treatment response will be determined according to the Clinical Global Impression Scale – Improvement (CGI-I), based upon clinical judgment and scores from relevant measures within the Secondary Endpoints subsection:*

- Clinical Global Impression Scale – Improvement (CGI-I): The CGI-I is a clinician rated global measure of improvement and is made up of a 7-point scale where: 1=very much improved, 2=much improved, 3=minimally improved, 4=no change, 5=minimally worse, 6=much worse, and 7=very much worse (69). The CGI-I has been used as an outcome measure in multiple clinical psychopharmacology trials and will be completed through expert consensus, including a team of child psychologists and psychiatrists with expertise in ASD, based upon scores from relevant measures and clinical judgment. This will be completed at the final study visit (Week 6).

#### Secondary Endpoints – Symptom Measurement

##### *Autism Measures*

- Behavioral Inflexibility Scale (BIS): The BIS is a newly developed parent-report measure designed to assess rigid patterns of behavior, commonly associated with ASD, in children and adolescents 3-18 years of age. The BIS includes 38 items rated on a 6-point Likert scale where 0=Not at all a problem and 5=Very severe or extreme problem. Psychometric properties resulting from initial evaluations of the measure are strong (70). The BIS will be completed by caregivers at the enrollment/baseline visit (or at the screening visit), at the final study visit (Week 6), and 6 weeks after medication discontinuation (optional).

- OSU Autism Clinical Global Impression-Severity and Improvement Subscales: The OSU Autism CGI-Severity and Improvement scales are adapted versions of the classic CGI-S and CGI-I developed by the OSU Research Unit on Pediatric Psychopharmacology (RUPP) to better account for autism symptoms in clinician ratings. The indications are more directly and specifically related to ASD compared to those in the CGI. Importantly, the OSU Autism CGI has been found reliable when used by experienced clinicians (73). The OSU Autism CGI-S will be completed by the research team at the enrollment/baseline visit and final visit (Week 6) to obtain an estimate of severity of ASD symptoms. The OSU Autism CGI-I will be completed in the final visit (Week 6) by the research team to quantify improvement in core ASD symptoms only. These uses are differentiated from our use of the CGI-S and the CGI-I in the current study, as both the CGI-S and CGI-I will be used to assign ratings to each participant's individualized target symptom domain whereas the OSU Autism CGI-S and OSU Autism CGI-I ratings will relate to ASD symptoms only.
- Repetitive Behavior Scale-Revised (RBS-R): The RBS-R is a questionnaire used to measure the range of RRBs expressed by individuals with ASD. The RBS-R consists of six subscales covering a range of RRB subtypes including: Stereotyped Behavior, Self-injurious Behavior, Compulsive Behavior, Routine Behavior, Sameness Behavior, and Restricted Behavior. The subscales have no overlap of item content, permitting differential identification and scoring of discrete varieties of RRB. The presence and frequency of behaviors are rated on a 4-point scale (ranging from 0=behavior does not occur to 3=behavior occurs and is a severe problem) (74-76). The RBS-R will be completed by caregivers at the enrollment/baseline visit (or at the screening visit), at the final study visit (Week 6), and 6 weeks after medication discontinuation (optional), and takes approximately 20 minutes to complete.
- Social Responsiveness Scale, 2nd Edition (SRS-2), School-Age Form: The SRS-2 is a measure of social impairment related to ASD in children aged 4 to 18 years old. Five domains are assessed including: Social Awareness, Social Cognition, Social Communication, Social Motivation, and Restricted Interests and Repetitive Behavior. Items are scored on a 4-point scale (ranging from 1=not true to 4=almost always true). Excellent psychometric properties have been previously established for the SRS for use in children and adults (77, 78). The SRS-2 will be administered at screening and at the final study visit (Week 6), and 6 weeks after medication discontinuation (optional). The SRS-2 takes approximately 20 minutes to complete.

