### 1.3 SCHEDULE OF ACTIVITIES (SOA)

Procedures	Screening	Study Visit 1 Enrollment/Baseline	Telephone Follow-Up 1	Study Visit 2	Telephone Follow-Up 2	Study Visit 3	Telephone Follow-Up 3	Study Visit 4 Final Study Visit	2-Week Post-Trial Telephone Follow-Up	4-Week Post-Trial Telephone Follow-Up	6-Week Post-Trial Follow-Up	3-Month Telephone Follow-Up(s) c
Informed consent and assent	X											
Demographics	X											
Medical, Psychiatric, and Treatment history	X											
Administer study intervention		X		X		X						
Concomitant medication review	X	X	X	X	X	X	X	X	X	X		X
Physical exam (including height and weight)	X*							X				
Vital signs	X*	X		X*		X*		X				
Test of hepatic and hematologic function a	X					X*		X				
Pregnancy test b	X											
Plasma for CBD levels								X				
Urine drug screen	X											
Adverse event review and evaluation			X	X	X	X	X	X	X	X		
UKU Side Effects Rating Scale				X		X		X				
Mock MRI scan	X											
MRI		X						X				
Aberrant Behavior Checklist (ABC)		X*						X			X	
Anxiety, Depression, and Mood Scale (ADAMS)		X*						X			X	
Anxiety Scale for Children – Autism Spectrum Disorder – Child version (ASC-ASD-C)		X*						X				
Anxiety Scale for Children – Autism Spectrum Disorder – Parent version (ASC-ASD-P)		X*						X			X	
Autism Diagnostic Observation Schedule – 2 nd Edition (ADOS-2)	X*											
Childhood Autism Rating Scale, 2nd Edition, High Functioning (CARS-2-HF)	X											
Autism Family Experience Questionnaire (AFEQ)		X*						X				
Autism Symptom Interview (ASI)	X											
Behavioral Inflexibility Scale (BIS)		X*						X			X	
Brief Observation of Social Communication-Change (BOSCC)		X						X				
Clinical Global Impression Scale – Improvement (CGI-I)								X				
Clinical Global Impression-Severity (CGI-S)	X	X						X				
Columbia-Suicide Severity Rating Scale (C-SSRS)	X	X		X		X		X				
Computerized Kiddie Schedule for Affective Disorders and Schizophrenia (KSADS-COMP)	X											
Home Situations Questionnaire – ASD (HSQ-ASD)		X*						X			X	
OSU Autism Clinical Global Impression: Severity Subscale	X	X						X				
OSU Autism Clinical Global Impression: Improvement Subscale								X				
Repetitive Behavior Scale – Revised (RBS-R)		X*						X			X	
Screen for Child Anxiety Related Disorders (SCARED), Parent Version		X*						X			X	
Sleep Disturbance Scale for Children (SDSC)		X*						X			X	
Social Responsiveness Scale, 2nd Edition (SRS-2)	X							X			X	

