### 3 OBJECTIVES AND ENDPOINTS

OBJECTIVES	ENDPOINTS	JUSTIFICATION FOR ENDPOINTS
Primary		
Determine the optimal dose of CBD in children and adolescents with ASD	Establishment of optimal dose of CBD in children and adolescents with ASD, defined as the dose at which the greatest proportion of participants respond. Discussed further in the Dosing and Administration section, the definition of treatment response will be individualized for each participant based upon a predetermined target symptom cluster.	Identification of the optimal dose of CBD (within the range tested) is desirable given the insufficient research in this area and the potential for dose-dependent inverted-U effects (2, 9).
Secondary		
Identify the primary outcome measure for a subsequent double-blind placebo-controlled RCT	Change in core and associated symptoms from baseline based upon measures developed to assess ASD symptoms, symptoms often associated with ASD, and global functioning including: 
 
- ABC Social Withdrawal and Irritability Subscales
 
- ASC-ASD-Child and Parent
 
- AFEQ
 
- ADAMS
 
- BIS
 
- CGI-I
 
- CGI-S
 
- HSQ-ASD
 
- OSU Autism CGI Severity
 
- OSU Autism CGI Improvement
 
- RBS-R
 
- SCARED
 
- SDSC
 
- SRS-2
 
- SWAN (Part 2 of the trial)
 
- Vineland-3
 
	Measures were selected because they have been widely used in prior trials in ASD (ABC, CGI, HSQ-ASD, OSU Autism CGI, RBS-R, SCARED, SRS-2, SWAN [Part 2], Vineland-3), or have been used in a recent trial of CBD in Fragile X syndrome (ADAMS) or have been used in medication trials more broadly (SDSC), or represent new and innovative tools available in the ASD field (ASC-ASD; AFEQ; BIS).
Tertiary/Exploratory		
Assess underlying brain mechanisms using MRI	Change in brain activity, indexed by resting-state functional connectivity. Otherwise, results will be reported	Inform the feasibility of incorporating biomarkers (e.g., resting-state functional

OBJECTIVES	ENDPOINTS	JUSTIFICATION FOR ENDPOINTS
	qualitatively (conducted at in-person visits only, if participants agree)	connectivity) in our future studies and potentially yield testable hypotheses.

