### 5 STUDY POPULATION

#### 5.1 INCLUSION CRITERIA

Patients who will be selected for this study will meet the following criteria:

- Male or female pediatric outpatients aged between and including 7 to 17.9 years old
- Diagnosis of ASD confirmed by the ADOS-2 or CARS-2-HF and DSM-5 criteria

- Part 2: Diagnosis of ADHD confirmed by clinician review of the K-SADS-COMP
- SRS-2 Total T-score of 66 or higher
- CGI-S score of 4 or higher
- Physical exam and laboratory results that are within normal range for their age
- Fluent speech
- Estimated IQ of at least 80
- Presence of a parent/legal guardian who is able to consent for their participation and complete assessments regarding the child's development and behavior throughout the study
  - Child Assent will be obtained.

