#### *General Functioning*

- Autism Family Experience Questionnaire (AFEQ): The AFEQ was developed to measure the impact of autism interventions on family experience and quality of life. Recent research on the AFEQ demonstrated the measure was sensitive to change in response to intervention in young children with ASD (91). The measure includes 48 items that make up four domains: Parent, Family, Child Development, and Child Symptoms. Ratings on each item can also be summed to equal a total score. The AFEQ will be administered to parents at the enrollment/baseline visit (or at the screening visit) and at the final visit (Week 6) and takes about 15 minutes to complete.
- Clinical Global Impression-Severity (CGI-S): The CGI-S reflects clinician impression of the participant’s current severity of illness on a 7-point scale ranging from 1=not at all ill to 7=among the most extremely ill (69). The CGI-S will be completed by the evaluating clinician at the screening visit, and by clinician consensus at the enrollment/baseline visit and the final study visit (Week 6).

Given the extent of the information we are requesting from caregivers, rating scales will be available to complete online from home during the time period between the screening and enrollment/baseline visits, and in the sixth week of treatment up until the final study visit. Caregivers can choose to complete these forms in the clinic or online. Caregivers can choose to complete these forms prior to their child being found eligible for participation, in the case the additional time makes completion of the measures more feasible for the caregiver and scheduling of subsequent visits more efficient. An eligible child will not be administered the study drug until all forms are submitted. If the caregiver does not complete the forms prior to coming to the final study visit, all forms must be completed at the clinic during that visit.

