- **Computerized Kiddie Schedule for Affective Disorders and Schizophrenia (KSADS-COMP)**: As described above, in Part 2 of the trial, the K-SADS-COMP will be administered at the screening visit and will also be used to confirm the presence of an ADHD diagnosis.
- **Wechsler Abbreviated Scale of Intelligence, Second Edition (WASI-II)**: The WASI-II was designed to swiftly and accurately assess cognitive functioning and has strong psychometric properties (95). The WASI-II, Two-Subtest Form will be administered in this study to obtain data on intellectual ability. This form consists of two subtests (i.e., Vocabulary and Matrix Reasoning) and takes approximately 10-20 minutes to complete. This will only be completed at screening. Estimated IQ must be at or above 80 to participate in the trial. As with the ADOS-2, the WASI-II will not be administered if a reliable and valid IQ assessment was performed by a qualified

professional and was documented within the previous 3 years of the screening visit or when the child was 6 years of age or older.

- Clinical Global Impression-Severity (CGI-S): Information regarding the CGI-S is provided within Section 8.1 Secondary Study Endpoints. Within the screening visit, patients must receive a rating of 4 (Moderately Ill) or higher on the CGI-S to participate in the trial.
- Social Responsiveness Scale, 2nd Edition (SRS-2), School-Age Form: Information regarding the SRS-2 is provided within Section 8.1 Secondary Study Endpoints. Patients must receive a total T-score of 66 to meet inclusionary criteria for participation in the study.

Further, in the case of virtual visits for participants who do not have prior documentation of an ADOS assessment, because confirming a diagnosis of ASD virtually is understudied, we will follow up cases for which clinicians report substantial uncertainty by administering a complete Autism Diagnostic Interview-Revised (ADI-R), the gold standard interview instrument for ASD that takes 1-3 hours to administer.

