#### 9.4.3 ANALYSIS OF THE SECONDARY ENDPOINT(S)

Our secondary objective is to quantify the effect size of changes in a wide range of candidate measures that may reveal response to CBD. Effect sizes and 95% confidence intervals will be reported for all measures obtained at enrollment/baseline and at the final visit (or last observation, in cases of early termination).

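### SRS-2 is the only change outcome whose baseline is its own qualifying score (T-score 66 or higher), so its effect size carries a small regression to the mean

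*Combined protocol and SAP*

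**What the plan says.** Section 5.1 lists "SRS-2 Total T-score of 66 or higher" among the inclusion criteria. Section 8.2 (Screening measures) applies this to the screening administration: "Patients must receive a total T-score of 66 to meet inclusionary criteria for participation in the study".

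Section 8.1 (Autism Measures) sets the timing: "The SRS-2 will be administered at screening and at the final study visit (Week 6", with a further optional administration six weeks after the drug is stopped. The Schedule of Activities agrees. The row "Social Responsiveness Scale, 2nd Edition (SRS-2" is marked at screening, Visit 4 and the six-week follow-up, and the Visit 1 cell is empty.

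Section 3 lists the SRS-2 among secondary endpoints defined as "Change in core and associated symptoms from baseline based upon measures developed to assess ASD symptoms". The objective attached to that list is to identify the primary outcome for a later placebo-controlled trial. Section 9.4.3 reports effect sizes and 95% confidence intervals for "all measures obtained at enrollment/baseline and at the final visit". Nothing names the screening score as the SRS-2 baseline.

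The CGI-S also has an entry cutoff (4 or higher), but Section 8.1 (General Functioning) has it rated by the evaluating clinician at screening "and by clinician consensus at the enrollment/baseline visit and the final study visit (Week 6". Its qualifying and baseline ratings are therefore separate.

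Section 8.2 allows more than 8 weeks between screening and enrollment. Eligibility is then confirmed by telephone, and no repeat SRS-2 is mentioned.

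**The concern.** When children are admitted because a score is high, and change is measured from that same score, part of the score is favourable error that will not recur. The group mean then falls at the next administration even if the drug does nothing. Section 4.1 describes a single-group study, so no control arm can absorb this fall.

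What is at stake is the comparison across scales. Section 4.1 says the effect sizes are meant to help choose the outcome measures of the next trial. A bias that acts directly on one core-symptom scale tilts that comparison toward the SRS-2. A qualifying score that predates the first dose by more than 8 weeks is also a weak measure of the child's state when treatment starts.

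**Working it through.** **1. Is the SRS-2 the only such outcome?** The measures that gate entry are the SRS-2, CGI-S, ADOS-2 or CARS-2-HF, the IQ estimate and, in Part 2, the K-SADS-COMP.

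- ADOS-2, CARS-2-HF, WASI-II and K-SADS-COMP are not change outcomes.
- CGI-S is a change outcome but is rated again at enrollment/baseline.
- The other caregiver scales may be completed at screening or baseline, but none has a cutoff.

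That leaves the SRS-2 as the only change outcome selected directly on its own baseline.

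**2. Inputs.** The cutoff of 66 is from Sections 5.1 and 8.2. The plan gives no SRS-2 mean, SD or retest correlation, and Section 9.2 states no sample-size method, so there is no figure of the plan's own to reproduce. Assumptions: scores normal before selection with SD 10, mean μ of 74 to 78, retest correlation r of 0.7 to 0.9, no drug effect.

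**3. Formula.** With a = (66 − μ)/SD and λ = φ(a)/(1 − Φ(a)):

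- spurious fall = (1 − r) × SD × λ
- SD of enrolled children's baseline = SD × √(1 + aλ − λ²)
- SD of change = √[(1 − r)² × (enrolled SD)² + SD² × (1 − r²)]

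**4. Mid case, μ = 74, r = 0.8.** a = −0.8; φ(a) = 0.290; 1 − Φ(a) = 0.788; λ = 0.368. Spurious fall = 0.2 × 10 × 0.368 = 0.74 T points. Enrolled SD = 10 × √(1 − 0.294 − 0.135) = 7.56. Ratio = 0.74/7.56 = 0.10.

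**5. Range.** The half-width is for a 95% interval on mean change with n = 30: 2.045 × SD of change/√30, divided by the enrolled SD.

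| μ | r | Pass 66 | Fall (T points) | Enrolled SD | Fall / enrolled SD | Half-width / enrolled SD |
|---|---|---|---|---|---|---|
| 74 | 0.7 | 79% | 1.10 | 7.56 | 0.15 | 0.37 |
| 74 | 0.8 | 79% | 0.74 | 7.56 | 0.10 | 0.31 |
| 74 | 0.9 | 79% | 0.37 | 7.56 | 0.05 | 0.22 |
| 78 | 0.7 | 88% | 0.66 | 8.30 | 0.08 | 0.34 |
| 78 | 0.9 | 88% | 0.22 | 8.30 | 0.03 | 0.20 |

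**6. Check against planned screening losses.** Section 5.4 expects about five children screened for each cohort of three, so about 2/5 = 40% lost for all reasons. With SD 10, a mean of 70 implies that 34% fail the SRS-2 alone, and a mean of 66 implies 50%. At r = 0.7 these give 0.25 and 0.40 SD. The second exceeds the planned loss from all causes. The first uses up nearly all of it, leaving little for IQ, laboratory results, medication, CGI-S and the other criteria. Means of 74 to 78 imply 12% to 21% failing on the SRS-2, which fits.

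**7. Effect of a repeat baseline.** A simulation with no drug effect, a stable true score and independent errors on each occasion gave these spurious changes from screening, in pre-selection SD units: 0.13 (60% pass, r = 0.8), 0.06 (60% pass, r = 0.9) and 0.04 (90% pass, r = 0.8). Measured from a repeated pre-dose score, each was 0.00.

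**The case against.** Four points can be made on the other side.

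*Other scales can regress too.* This stands. Any scale correlated with the entry criteria can fall a little; SWAN beside the K-SADS-COMP requirement in Part 2 is an obvious case. The CGI-S baseline consensus draws on informant report and battery scores, and nothing says the team is unaware of the screening rating. A reader might infer that only the SRS-2 would improve with no drug effect. The documents do not support that. What is particular to the SRS-2 is direct selection on its own baseline, so the contrast is one of degree.

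*Section 9.4.3 does not really exclude the SRS-2.* This also stands. A reader might infer that the wording drops the scale from the analysis, because it is not obtained at enrollment/baseline. Section 3 lists it as a change endpoint, and Section 7.1 includes it in the assessments at discontinuation. Elsewhere the protocol calls the screening blood draw a baseline draw. The same literal reading would also remove the CGI-I and OSU Autism CGI-I, which are rated only at the final visit. The sections need reconciling, but the intent is clear.

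*The bias is small beside the sampling error.* It is, under the assumptions above: 0.10 SD against a half-width of 0.31 in the mid case. Section 4.1 calls all endpoints exploratory and Section 9.4.3 sets no ranking rule, so it is not shown that any choice of outcome would change. But the direction is known and a larger sample would not remove it, so the interval does not account for it.

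*A clean repeat baseline would come late.* The summary of changes mentions data on 19 participants, so at most 30 − 19 = 11 remain. Restricting the comparison to them would widen the half-width to about 0.36 to 0.67 SD (2.228 × SD of change/√11, same assumptions), well above the bias removed. All would be Part 2 children with ASD and ADHD on one dose. This is a sound reason to keep every child in the analysis.

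**Conclusion.** The point holds in a limited form. The SRS-2 qualifying score doubles as its baseline, there is no control arm, and its effect size therefore leans toward improvement. For retest correlation below 1 and a stable true score the direction is not in doubt. The size is not fixed by the documents: about 0.2 to 1.1 T points, or 0.03 to 0.15 baseline SD, if scores before selection are normal with SD 10 and mean 74 to 78 and the retest correlation is 0.7 to 0.9. Figures of 0.25 to 0.40 SD might be inferred from lower means, but these fit poorly with the planned screening losses. Those losses are themselves a planning ratio, not observed data. The consequence is a slight advantage for the SRS-2 in the comparison of scales. It is worth a low-cost correction and a label, and does not invalidate the secondary analysis.

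**What to change.** 1. **Children not yet dosed.** Add the SRS-2 to the Visit 1 caregiver battery, which caregivers can already complete online before the first dose. It must be a second administration, separate from the qualifying one. Use it as baseline and keep the screening score for eligibility only.
2. **Children already enrolled.** Keep the screening score as baseline and keep them in the analysis.
3. **Reporting.** Label the SRS-2 effect size as subject to regression to the mean. Give a sensitivity correction for screening-score baselines, (1 − r) × (mean screening score of enrolled children − mean before selection), over a stated range of r and with the source or assumed value of the pre-selection mean given. Report separately the result for children with a Visit 1 baseline.
4. **Section 9.4.3.** State which score is the SRS-2 baseline for each group, so that it agrees with Section 3, and amend the Schedule of Activities to match.

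The cost is about 20 minutes of caregiver time (the protocol's own estimate) for each of at most 11 remaining children, in an amendment meant to reduce caregiver burden, plus short text changes. Baseline timing will be mixed across the sample, and the subgroup with a Visit 1 baseline will be too small to stand alone. If errors at screening and Visit 1 are correlated, for instance because the two are close together, some regression will remain.
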